9. RESEARCH METHODS

9.1 STUDY DESIGN

This is a non-interventional, multi-country, multi-site study based on existing data from medical records of patients treated with Gi(l)otrif[®] as part of the routine treatment according to the approved label.

Key study outcomes are:

- Effects of Gi(l)otrif[®] dose reduction on frequency of ADRs, and time on treatment, time to progression
- Proportion of patients starting with modified Gi(l)otrif[®] dose and the underlying reason(s)

Data on diagnosis, gender, date of birth, ethnicity, body weight and height, Eastern Cooperative Oncology Group performance score (ECOG) ([R14-0080](#)), EGFR mutational subgroup (Del19/L858R), starting dose of Gi(l)otrif[®], start date of Gi(l)otrif[®] treatment, dose modifications with date, ADRs, concomitant medications (limited to medication for management of diarrhea, skin effects, mucositis/stomatitis as dichotomous variables (e.g. received anti-diarrhea medication yes/no), reason for dose modification of Gi(l)otrif[®], treatment duration of Gi(l)otrif[®], time to progression and type of progression (clinical, radiographic or both clinical/radiographic progression) will be collected from patients medical records by investigators.

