9.3 VARIABLES

Data will be documented from the date of first dose of Gi(l)otrif[®] treatment until the date of last dose of Gi(l)otrif[®] treatment or end of data collection whichever occurs first.

During the data collection period, the following data will be collected from medical records in an eCRF by investigators during the study:

- Informed consent
- Diagnosis
- Demographics (gender, date of birth, ethnicity)
- Body weight and height at start of Gi(l)otrif[®] treatment
- ECOG performance score at start of Gi(l)otrif[®] treatment
- EGFR mutational subgroup (Del19/L858R)
- Starting dose of Gi(l)otrif[®]
- Start date of Gi(l)otrif[®] treatment
- End date of Gi(l)otrif[®] treatment
- Gi(l)otrif[®] dose modification(s) and date(s)
- ADRs
- Concomitant medications (limited to medication for management of diarrhea, skin effects, mucositis/stomatitis as dichotomous variables (e.g. received anti-diarrhea medication yes/no))
- Reason for dose modification(s)
- Date of progression
- Type of progression:
 - a. clinical
 - b. radiographic
 - c. both clinical/radiographic progression

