9.10.4 Patient completion

The collection of the data of patients will continue until end of data collection or withdrawal of consent which occurs first.

At the earliest of the above criteria, the Patient Completion information should be completed in the eCRF.

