9.12 BIAS

Methodological efforts have been taken to minimize selection bias: these efforts include the recommendation to include consecutive patients meeting each of the inclusion criteria and none of the exclusion criteria. In addition, this possible selection bias may be limited by the retrospective aspect of the data collection, data that have been already collected at the time of the study.

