11.2 ADVERSE EVENT AND SERIOUS ADVERSE EVENT COLLECTION AND REPORTING

The investigator shall maintain and keep detailed records of all AEs in their patient files.

Collection of AEs

The study design is of non-interventional nature and the study is conducted within the conditions of the approved marketing authorization. Sufficient data from controlled interventional trials are available to support the evidence on the safety and efficacy of the studied BI drug. For this reason the following AE collection and reporting requirements have been defined.

The following must be collected by the investigator in the eCRF from signing the informed consent onwards until the end of the study:

- all ADRs (serious and non-serious)
- all AEs with fatal outcome
- for Japan: an AE which possibly leads to disability will be reported as an SAE

All ADRs, including those persisting after study completion must be followed up until they are resolved, have been sufficiently characterized, or no further information can be obtained.

The investigator carefully assesses whether an AE constitutes an ADR using the information below.

Causal relationship of AEs

The definition of an adverse reaction implies at least a reasonable possibility of a causal relationship between a suspected medicinal product and an adverse event (AE). An adverse reaction, in contrast to an AE, is characterized by the fact that a causal relationship between a medicinal product and an occurrence is suspected.

Medical judgment should be used to determine the relationship, considering all relevant factors, including pattern of reaction, temporal relationship, de-challenge or re-challenge, confounding factors such as concomitant medication, concomitant diseases and relevant history.

Arguments that may suggest a **reasonable causal relationship** could be:

- The event is **consistent with the known pharmacology** of the drug
- The event is known to be caused by or **attributed to the drug class**.
- **A plausible time to onset of the event** relative to the time of drug exposure.
- Evidence that the **event is reproducible** when the drug is re-introduced

Protocol for non-interventional studies based on existing data

BI Study Number 1200.270

c09038525-01

Proprietary confidential information © 2016 Boehringer Ingelheim International GmbH or one or more of its affiliated companies

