The following must be reported by the investigator on the NIS AE form from signing the informed consent onwards until the end of the study:

Type of Report	Timeline
----------------	----------

Protocol for non-interventional studies based on existing data

BI Study Number 1200.270**c09038525-01**

Proprietary confidential information © 2016 Boehringer Ingelheim International GmbH or one or more of its affiliated companies

All Serious Adverse Drug Reactions (SADRs) associated with Gi(l)otrif [®]	immediately within 24 hours
All AEs with fatal outcome in patients exposed to Gi(l)otrif [®]	immediately within 24 hours
For Japan: AE which possibly leads to disability in patients exposed to Gi(l)otrif [®]	immediately within 24 hours
All non-serious ADRs associated with Gi(l)otrif [®]	7 calendar days
All pregnancy monitoring forms	7 calendar days

The same timelines apply if follow-up information becomes available for the respective events. In specific occasions the physician could inform the sponsor upfront via telephone. This does not replace the requirement to complete and fax the NIS AE form.

Information required

For each reportable AE, the investigator should provide the information requested on the appropriate eCRF pages and the NIS AE form.

Reporting of related AEs associated with any other BI drug

The investigator is encouraged to report all AEs related to any BI drug other than Gi(l)otrif[®] according to the local regulatory requirements for spontaneous AE reporting at the investigator's discretion by using the locally established routes and AE report forms. The term AE includes drug exposure during pregnancy, and, regardless of whether an AE occurred or not, any abuse, off-label use, misuse, medication error, occupational exposure, lack of effect, and unexpected benefit.

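### The plan does not settle whether ADR data for patients still on treatment stop at chart abstraction or continue under prompted reporting; if they continue, capture can be fuller after an early dose modification than before it

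*Protocol*

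**What the plan says.** Some passages keep each patient's window open after inclusion:

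- Section 9.3 runs documentation from first dose to the last dose of "treatment or end of data collection whichever occurs first". Section 6 dates data collection from 31 May to 31 December 2016.
- Section 9.10.4: "The collection of the data of patients will continue until end of data collection or withdrawal of consent which occurs first".
- Section 11.2 has the investigator enter all ADRs and all fatal AEs "in the eCRF from signing the informed consent onwards until the end of the study". It adds: "All ADRs, including those persisting after study completion must be followed up until they are resolved" (or are characterised, or nothing more can be learned).
- The same section sets reporting deadlines: "The following must be reported by the investigator on the NIS AE form from signing the informed consent onwards until the end of the study". These are 24 hours for serious ADRs and fatal AEs, and 7 calendar days for non-serious ADRs.

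Other passages describe records that already exist:

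- Section 9.1 calls this a "study based on existing data from medical records of patients", and section 9.2.2 names existing medical records as the source.
- Section 9.7.1 and SAP section 1 censor patients still on treatment at the data collection date, which neither document defines.
- Section 9.9 says nothing further is gathered for the study. Sections 9.9 and 9.12 both refer to "data that have been already collected at the time of the study".

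Two further rules matter. Section 9.2.1 admits patients still on treatment only if they have had at least 6 months of it. Section 9.7.1 limits the pre/post-modification ADR analysis to patients modified within the first 6 months, and splits it at 40 mg and at 30 mg.

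**The concern.** The effect of dose modification on the frequency and severity of ADRs is the first element of the primary objective. The within-patient pre/post comparison is the analysis that addresses it, set descriptively beside LUX-Lung 3.

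Before inclusion, an ADR is known only if someone wrote it in the chart. After inclusion, on the literal reading, an investigator who knows the study question must enter, follow up and report every ADR. If that second kind of time can fall on only one side of the modification, the two periods are not observed in the same way. The fall in ADRs would be understated, and routine practice could look worse than the trial partly because of how events were recorded. Neither section 9.9 nor section 9.12 mentions this.

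**Working it through.** The plan states no figure on this point. The steps below check the timing logic and then bound the size.

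**1. Timing.** Let *m* be the month of the first modification and *T* the month on treatment at inclusion. Section 9.7.1 gives *m* ≤ 6. Section 9.2.1 gives *T* ≥ 6 for patients still on treatment, taking the criterion as met at inclusion. So *T* ≥ *m*, and no post-inclusion time precedes the first modification. Patients who stopped before inclusion add no post-inclusion treatment time.

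**2. Longest possible accrual.** 31 May to 31 December 2016 is 214 days, and 214/30.44 = 7.0 months.

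**3. Patients affected.** Section 7 gives 53% reduced in LUX-Lung 3 (122/229 = 53.3%, which agrees), 86% of them within 6 months. Applied to the planned 200: 200 × 122/229 × 0.86 ≈ 92. If 20% to 50% of these are still on treatment at inclusion (assumed), 18 to 46 patients are affected.

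**4. Share of post-modification time under prompted reporting.** With *a* months of accrual, *w* = *a*/(*T* + *a* − *m*). Taking *m* = 2 (assumed):

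| Inclusion at month | *a* = 3.5 | *a* = 7 |
|---|---|---|
| 6 | 3.5/7.5 = 47% | 7/11 = 64% |
| 12 | 3.5/13.5 = 26% | 7/17 = 41% |
| 18 | 3.5/19.5 = 18% | 7/23 = 30% |

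The matching share of pre-modification time is 0% in every case.

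**5. Effect on the contrast.** Suppose true incidence is equal in both periods, charts capture a fraction *c* of ADRs, prompted reporting captures *p*, and a share *s* of the compared patients is still on treatment. The apparent post/pre ratio is

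1 + *s* × *w* × (*p* − *c*)/*c*.

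All four inputs are assumptions:

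| *c*, *p* | *s* = 0.20, *w* = 0.25 | *s* = 0.50, *w* = 0.50 |
|---|---|---|
| 0.60, 0.90 | 1.025 | 1.125 |
| 0.70, 0.90 | 1.014 | 1.071 |
| 0.80, 0.95 | 1.009 | 1.047 |

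The range is 1.01 to 1.13. If charts are abstracted once soon after inclusion, *w* approaches 0 and the ratio approaches 1.

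**6. Scale.** LUX-Lung 3 diarrhea fell from 99.2% to 46.7% after reduction (section 7), a fall of 52.5 points. Raising 46.7% by 0.9% to 12.5% adds about 0.4 to 5.8 points. This treats a per-event ratio as if it applied to the percentage of patients, so it shows order of size only.

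**7. Undated ADRs.** The SAP rule for a wholly missing onset starts the interval at the earlier of the AE end date and the consent date. Take a hypothetical patient with first dose on 1 June 2015, modification on 1 August 2015, consent on 15 June 2016 and last visit on 1 December 2016. An ADR with neither onset nor end date is imputed to 15 June 2016, after the modification. Where consent is waived, the rule has no consent date to use.

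**The case against.** The case for a narrower point is strong, and much of it stands.

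- **Single abstraction is a fair reading.** Section 9.2.2 has existing data and one site visit after collection, and section 9.9 rules out additional data. Section 9.10.5 speaks of the end of collection of the last patient's data, so the phrase can be a patient-level event. On that reading little time accrues. The duties in sections 9.10.4 and 11.2 still point the other way, so the text conflicts.
- **A reader might infer that all post-inclusion time of every ongoing patient is post-modification.** The documents do not support this. Patients never modified, or first modified after 6 months, are outside the comparison. Because section 9.7.1 also splits by dose level, time after re-escalation may count with the higher dose. The statement holds for calendar order only.
- **A reader might infer that the bias safeguard in sections 9.9 and 9.12 fails.** Those sections use the already-collected argument against selection bias only, and later accrual does not change who was selected. They are silent on ascertainment rather than wrong about it.
- **A reader might compute a larger bias from one patient.** With 9 charted post-modification months, 5.8 prompted months, and capture of 70% and 100% (all assumed), (9 × 0.70 + 5.8 × 1.00)/14.8 = 0.82, and 0.82/0.70 = 1.17. That 17% describes one ongoing patient, not the cohort.
- **The consequence is limited.** The analysis is descriptive, the reference falls are large, and the direction works against showing a benefit. The outcome counts patients, so one charted episode already counts and the shift may be smaller than the per-event ratio.

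**Conclusion.** The point holds in a limited form. The protocol gives two incompatible accounts of when ADR data stop for patients still on treatment, and they must be reconciled. If data continue after inclusion, then for ongoing patients modified within 6 months the prompted time lies wholly after the first modification, so capture can be fuller on that side.

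The likely result is a modest understatement of the fall in ADRs. The apparent post-modification figure rises by about 1% to 13% in relative terms across the cohort, and by close to nothing under prompt single abstraction. That range assumes chart capture of 60% to 80%, prompted capture of 90% to 95%, 20% to 50% still on treatment, and 25% to 50% of their post-modification time under prompted reporting. The documents supply none of these. The change is worth making because the difference runs in one direction, touches the primary objective and is cheap to remove.

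**What to change.** - In Protocol sections 9.3 and 9.7.1, and in the SAP, define one ADR cut-off date per patient, such as the date of inclusion or of chart abstraction. Use the same definition in every country, including those with a consent waiver. State whether documentation continues after it, and bring sections 9.2.2, 9.9, 9.10.4 and 11.2 into line.
- Flag each ADR by onset on or before that date versus after it. Give ADRs with no onset or end date their own category, since the SAP rule would otherwise place them at consent.
- Run the pre/post-modification ADR analysis on ADRs and exposure up to the cut-off, with the all-data version alongside.
- Keep all ADRs in the overall ADR percentages. Leave safety reporting and the time-to-event analyses unchanged.
- Add the ascertainment limitation to sections 9.9 and 9.12.

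The cost is some wording, one date field and a filter. The restricted analysis loses some post-modification follow-up, at most about 7 months per ongoing patient, which is why the all-data version should stay beside it.

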9.3.1 Exposures

Patients were/are treated with Gi(l)otrif[®] 50mg, 40mg, 30mg, 20mg tablet once daily as indicated in the approved labels of Gi(l)otrif[®].

The recommended starting dose of Gi(l)otrif[®] is 40mg once daily. A modified starting dose of Gi(l)otrif[®] per objective would be considered as any other dose different than 40mg once daily.

The Summaries of Product Characteristics on Gi(l)otrif[®] is contained in the NIS ISF in the “Summary of Product Characteristics” section.

9.3.2 Outcomes

9.3.2.1 Primary outcomes

Safety outcomes:

- Percentage of subjects with adverse drug reactions (ADRs) by severity class

Effectiveness outcomes:

- Time on treatment with Gi(1)otrif[®]
- Time to progression with Gi(1)otrif[®]

9.3.2.2 Secondary outcomes

- Percentage of subjects with a modified starting dose of Gi(1)otrif[®]
- Reasons of modifying starting dose

9.3.2.3 Further outcomes

n.a

9.3.3 Covariates

n.a

9.4 DATA SOURCES

NIS based on existing data from patients' medical records. Data will be collected in the eCRF. SDV will be performed on about 30% of included patients.

9.5 STUDY SIZE

The post-hoc analysis of LUX-Lung 3 providing the rationale for this study was based on 229 patients with 53% patients experiencing dose reduction. With a sample size of 200 we would be in the same range as in the LUX-Lung 3 analysis which provided robust data. It will be sufficient to analyse the effects of dose modification on patients' safety and effectiveness and to compare it with data from LUX-Lung 3 trial descriptively.

Based on feedback from physicians we expect 25-30% patients starting with a lower dose.

There will be around 50 patients starting with a modified dose, and around half of them with further de-/escalation. This is a sufficient sample size to get some impression on the reasons of a modified starting dose in real-world setting.

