	
 1. EGFR mutated (common mutations), TKI-naïve advanced NSCLC treated with Gi(1)otrif[®] as the first-line treatment for NSCLC within the approved label will be included 2. Patients treated within clinical trials are excluded 3. Patients still on treatment with Gi(1)otrif[®] will be excluded unless treatment period is ≥ 6 months
Variables:	
Primary outcomes:
 
Safety outcomes:
 
Percentage of subjects with adverse drug reactions by severity class
 
Effectiveness outcomes:
 
Time on treatment with Gi(1)otrif[®]
 
Time to progression with Gi(1)otrif[®]

Data sources:	NIS based on existing data from medical records of patients.
Study size:	At least 200 patients. ≥ 200 patients are planned based on feasibility aspects and assumptions.
Data analysis:	
Safety data will be analysed in a descriptive manner. Incidence and severity of adverse drug reactions will be summarized and displayed. For patients who have dose modifications, frequency and severity of the most common AEs pre- and post-dose modification will be summarized and displayed.
 
For effectiveness analysis, both time on treatment and time to progression will be estimated using Kaplan-Meier method, and the median along with two-sided 95% CI will be displayed (use the Greenwood's formula for estimation of standard errors). Log-rank test will be applied to compare between patients with and without dose modifications.

Milestones:	
Start of data collection in May 2016
 
End of data collection in December 2016
 
Final report of study results expected in March 2017

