Afatinib 40 mg/day (oral) is approved for the treatment of patients with advanced EGFRm+ NSCLC. Dose adjustments are recommended based on pre-defined tolerability criteria. A post-hoc analyses of the effects of afatinib dose reduction on adverse events (AEs), pharmacokinetics (PK) and PFS in the phase III LUX-Lung 3 trial showed that dose reductions occurred in 53% (122/229) of patients; the majority (86%) within the first 6 months of treatment. In patients who dose reduced, decreases in the incidences of drug-related all grade (grade \geq 3) AEs were 99.2% (20.5%) to 46.7% (4.1%) for diarrhea, 88.5% (26.2%) to 38.5% (3.3%) for rash/acne, 77.0% (12.3%) to 27.9% (0%) for stomatitis, and 44.3% (16.4%) to 36.9% (4.9%) for nail effects. Dose reductions tended to be more common in female patients, older patients, patients of Eastern Asian ethnicity, and patients with lower body weight. Dose reduction was more likely in patients with higher plasma concentrations of afatinib. On Day 43, patients who dose reduced to 30 mg \geq 4 days previously (n=38) had geometric mean plasma afatinib concentrations of 24.4 ng/mL, vs 23.7 ng/mL in patients who remained on the 40 mg dose (n=126). Median PFS was 11.3 months in patients who dose reduced during the first 6 months of treatment, vs 11.0 months in patients who did not (HR=1.25 [95% CI, 0.91–1.72]). [ASCO 2015, Yang et al, # 8073] ([P15-05676](#)).

Post-hoc analyses from LUX-Lung 3 suggest that tolerability-guided dose adjustment of afatinib is an effective measure to reduce treatment-related AEs without affecting therapeutic efficacy:

- The frequency and severity of treatment-related AEs was lower following dose reduction
- Tolerability-guided dose modification reduced the inter-patient variability of afatinib exposure, while maintaining efficacious plasma levels
- Efficacy outcomes were similar in patients who dose reduced due to AEs versus those who did not

This real-world data (RWD) study will help to understand if dose modifications are done similar as in LUX-Lung 3 trial and if the outcome on safety and effectiveness are as in trial settings.

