9.7 DATA ANALYSIS

9.7.1 Main analysis

All collected data will be analysed separately for patients starting with 40mg and \leq 30mg. Although due to anticipated low sample size in patients starting with \leq 30mg, it will be mainly for exploratory purpose. Baseline demographics will be analysed with descriptive statistics (N, median, mean, 25%, 75% percentile, SD) and compared descriptively between patients who have dose modifications within the first 6 months of Gi(l)otrif[®] treatment and those who do not. All the demographics, safety and efficacy data from this study in real-world setting will be compared with data from LUX-Lung 3 trial in descriptive manner.

Analysis of Safety:

[figure not shown]
Safety analysis will include all patients treated with Gi(l)otrif[®] and be descriptive in nature. Incidence and severity of ADRs according to Common Terminology Criteria for Adverse Events (CTCAE) criteria (version 4.0) ([R15-5988](#)) when available will be summarized and displayed in number/percentage. For patients who had Gi(l)otrif[®] dose modifications within the first 6 months of Gi(l)otrif[®] treatment, frequency and severity of the common ADRs pre- and post-dose modification will be analysed (\geq 40mg vs $<$ 40mg; and \geq 30mg vs $<$ 30mg). Missing or incomplete ADR dates will be imputed according to BI internal SOPs.

Analysis of Effectiveness:

Effectiveness analysis will include all patients treated with Gi(l)otrif[®]. Time on treatment is from the date of first dose of Gi(l)otrif[®] treatment to the date of last dose of Gi(l)otrif[®] treatment. Time to progression is from the date of first dose of Gi(l)otrif[®] treatment to the earliest date of documented progression (clinical, radiographic or both clinical/radiographic progression) or death. Time on treatment and time to progression will be estimated using Kaplan-Meier method, and the median along with two-sided 95% CI will be displayed (use the Greenwood's formula for estimation of standard errors). Log-rank test will be applied to compare between patients with and without dose modifications. Time on treatment and time to progression will be compared between patients who dose reduced to $<$ 40 mg within the first 6 months of Gi(l)otrif[®] treatment and those who remained on Gi(l)otrif[®] 40 mg once daily. This is in analogy to the analysis made on LUX-Lung 3 where a cut-off of 6 months was used as most dose reductions occur during this time.

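### Section 9.5 sets 200 enrolled patients against LUX-Lung 3's 229, but only about 140–150 of the 200 can enter the matching dose-reduction contrast

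*Protocol*

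**What the plan says.** Protocol section 9.5 takes its reference from the LUX-Lung 3 post-hoc analysis, which "was based on 229 patients with 53% patients experiencing dose reduction". It then argues: "With a sample size of 200 we would be in the same range as in the LUX-Lung 3 analysis which provided robust data". From this it concludes that the size is adequate for studying what dose modification does to safety and effectiveness, and for a descriptive comparison with LUX-Lung 3. It gives no alpha, power, target effect or precision.

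The same section continues: "Based on feedback from physicians we expect 25-30% patients starting with a lower dose", and "There will be around 50 patients starting with a modified dose, and around half of them with further de-/escalation".

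Section 9.7.1 splits the analysis by starting dose: "All collected data will be analysed separately for patients starting with 40mg and" those starting at 30 mg or less. It describes the lower-dose group as mainly exploratory because few patients are expected. For time on treatment and time to progression it names one contrast as the analogue of LUX-Lung 3: patients reduced below 40 mg in the first 6 months against those who stayed on 40 mg. The planned outputs are Kaplan-Meier medians with 95% confidence intervals and a log-rank test. Neither the protocol nor the SAP plans a hazard ratio.

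Section 7 supplies the LUX-Lung 3 figures: "dose reductions occurred in 53% (122/229) of patients; the majority (86%) within the first 6 months of treatment". For progression-free survival by early reduction it reports "HR=1.25 [95% CI, 0.91–1.72".

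**The concern.** The two numbers in section 9.5 are not counted on the same basis. The 229 is the number analysed in LUX-Lung 3 for the effect of dose reduction. The 200 is everyone enrolled, including the quarter or more expected to start on a lower dose. A patient who starts at 30 mg or less cannot have remained on 40 mg, and is analysed apart from the 40 mg starters. Such a patient therefore has no place in the contrast that is meant to mirror LUX-Lung 3.

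What is at stake is how the result will be read. Section 7 already takes the LUX-Lung 3 comparison as showing similar efficacy in reducers and non-reducers, although its interval reaches a hazard ratio of 1.72. A study declared large enough in advance, with fewer patients in the same contrast, could well return a non-significant log-rank test. That result could then be cited as confirmation when it mostly reflects limited information.

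**Working it through.** **The plan's own figures.** No formula stands behind 200, so it cannot be reproduced. The component figures can be checked:

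- 122/229 = 53.3%, which matches the stated 53%.
- 200 × 0.25 = 50, which matches the stated number of modified starters. 200 × 0.30 = 60, so that number reflects only the lower end of the 25–30% expectation.

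**Patients available for the contrast at 200 enrolled.**

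- 40 mg starters: 200 × (1 − 0.30) = 140 to 200 × (1 − 0.25) = 150.
- Relative to 229: 140/229 = 61% and 150/229 = 66%, so 34–39% fewer.
- Patients who start on 40 mg and escalate fit neither arm, so the usable number could be somewhat lower.

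**Early reducers, if LUX-Lung 3 rates apply.**

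- LUX-Lung 3: 0.86 × 122 = 104.9, or 45.8% of 229.
- Here: 0.458 × 140 = 64 to 0.458 × 150 = 69.

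**Precision.** A hazard ratio is used only as a yardstick, because it is the one measure of this contrast for which section 7 gives an interval.

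- Standard error (SE) of the log hazard ratio in LUX-Lung 3: ln(1.72/0.91)/(2 × 1.96) = 0.162.
- Implied events, from SE² = 1/[D × p × (1 − p)] with p = 0.458: D = 1/(0.1624² × 0.458 × 0.542) ≈ 153, and 153/229 ≈ 67%. This takes all 229 patients to be in that comparison; section 7 gives no separate number for it.
- At the same split and event fraction, the SE scales as √(229/n).

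| Patients in contrast | Early reducers | Events | SE | Excess over LUX-Lung 3 | Illustrative 95% CI around 1.25 |
|---|---|---|---|---|---|
| 229 (LUX-Lung 3) | 105 | 153 | 0.162 | – | 0.91–1.72 |
| 200 (if all counted) | 92 | 133 | 0.174 | 7% | 0.89–1.76 |
| 150 | 69 | 100 | 0.201 | 24% | 0.84–1.85 |
| 140 | 64 | 93 | 0.208 | 28% | 0.83–1.88 |
| 225 (75% of 300) | 103 | 150 | 0.164 | 1% | 0.91–1.72 |
| 210 (70% of 300) | 96 | 140 | 0.170 | 4% | 0.90–1.74 |

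The 300 is the upper site expectation in section 9.2: 30 sites × 10 patients. The lower end is 25 × 8 = 200.

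**Range over the assumed inputs.** The documents give no real-world event fraction or reduction rate. For 140–150 patients, with event fractions of 50–90% and early-reducer shares of 30–53%, the extremes are:

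- 140 patients, 50% events, 30% reducers: 1/√(0.5 × 140 × 0.3 × 0.7) = 0.261, which is 61% above 0.162.
- 150 patients, 90% events, 53% reducers: 1/√(0.9 × 150 × 0.53 × 0.47) = 0.172, which is 6% above 0.162.

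The loss from 200 to 140–150 patients by itself inflates the SE by √(200/150) = 1.15 to √(200/140) = 1.20, whatever common event fraction and split are assumed.

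**The case against.** The strongest reply is that section 9.5 promises very little. The study is descriptive, the ENCePP checklist (item 2.1.5) records that there is no prior hypothesis, and 200 is only 13% below 229. This stands in part. A reader might infer that the protocol promises LUX-Lung 3 precision, or that a power calculation has gone wrong. The documents support neither: no precision target is stated, and there is no power calculation to be wrong. Section 9.5 does, however, claim adequacy for effectiveness on the strength of the 229, and section 9.7.1 attaches a log-rank test.

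Second, 200 is a floor. The abstract says "At least 200 patients", and section 9.2 is compatible with about 300, at which the gap nearly closes. It would therefore go too far to infer that the design cannot reach LUX-Lung 3's information. But section 9.5 argues from 200, and nothing commits the sponsor to more or sets a minimum number of 40 mg starters.

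Third, section 9.7.1 says that the effectiveness analysis includes all treated patients, and it has a general log-rank comparison of patients with and without dose modification. So it would be wrong to say that every effectiveness analysis is confined to 40 mg starters. That broader comparison is not the LUX-Lung 3 analogue, though, and so does not rescue the comparison of 200 with 229.

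Fourth, the 24–28% rests on a back-calculated event fraction and on LUX-Lung 3 reduction rates. That is correct, and is why the range is shown.

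Finally, a reader might take the word robust in section 9.5 as a claim about this study. It describes the LUX-Lung 3 data and is not at issue here.

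**Conclusion.** The point holds as a gap in the size justification. At the 200 patients on which section 9.5 argues, the like-for-like number for the LUX-Lung 3 contrast is 140–150. That follows from the protocol's own figures and needs no outside assumption.

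The loss of precision is conditional. It is 24–28% on the standard error if LUX-Lung 3's early-reduction rate and implied event fraction carry over, and 6–61% over the wider range of inputs. Every combination examined at 140–150 patients is less precise than LUX-Lung 3. At 300 enrolled, with LUX-Lung 3 rates, the difference is 1–4% and of no practical importance.

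The same-range statement is fair for the total cohort. It is not fair for this contrast at the minimum enrolment.

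**What to change.** Revise section 9.5 as follows:

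- Give the expected number of 40 mg starters (140–150 at 200 enrolled; 210–225 at 300) and of early reducers (about 64–69 and 96–103, if LUX-Lung 3 rates apply).
- State that at the minimum enrolment the contrast of early reduction versus remaining on 40 mg will be less precise than in LUX-Lung 3. Show the assumptions and the range.
- Limit the same-range and adequacy statements to the total cohort and the descriptive comparison.
- Add that a non-significant log-rank result is not evidence that effectiveness is unaffected.
- Label any hazard-ratio interval, such as 0.83–1.88 around 1.25 for 140 patients, as illustrative, because section 9.7.1 plans no hazard ratio.
- Reconcile the figure of around 50 modified starters with the 25–30% range, which gives 50–60.

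The cost is protocol wording only, with no extra patients and no new analysis. The price is a less favourable statement of what the minimum size can deliver.
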